Hypothesis #1B: *Whole blood resuscitation will be associated with a lower incidence of 12 hour and 24 hour mortality, a lower incidence of death from exsanguination, incidence of MOF, nosocomial infection, improved transfusion ratios, lower overall blood transfusion requirements and shorter time to hemostasis as compared to those resuscitated with component therapy.*

Hypothesis #1C: *Whole blood resuscitation will be associated with an improved Glasgow Outcome Score-Extended at 6 months post injury as compared to those resuscitated with component therapy in patients with traumatic brain injury.*

Hypothesis #2A: *A nadir prehospital and acute phase resuscitation systolic blood pressure greater than or equal to 120 mmHg will be associated with improved traumatic brain injury outcomes at discharge and at 6 months.*

Linking Investigations in Trauma and Emergency Services

Task Order 2: Shock, Whole blood and Assessment of TBI (SWAT)

Hypothesis #2B: *The magnitude of the dose depth curve of systolic blood pressure during the prehospital and acute phase resuscitation will be associated with neurological outcome differences at discharge and at 6 months following traumatic brain injury.*

Research Design and Methods

Study Design: The LITES Network will perform a multicenter, prospective, observational cohort study over a 4 year period to determine the impact of whole blood resuscitation in trauma patients with hemorrhagic shock at risk of large volume resuscitation with and without TBI. Early whole blood resuscitation will be compared to standard component resuscitation. The study will also further characterize blood pressure and resuscitation endpoints in poly-trauma patients with traumatic brain injury. Six trauma sites with appropriate characteristics will be selected from network sites across the country. (Figure 2)

Figure 2

Study Setting: The study will be performed utilizing busy level I trauma centers from within the LITES Network located across the country, at sites where either whole blood has currently been incorporated into standard of care or where component blood transfusion is being utilized for patients in hemorrhagic shock at risk for large volume resuscitation. Due to the paucity of trauma centers who are currently utilizing whole blood for trauma patients as standard of care, the potential to incorporate additional sites may be required over time.

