Component Transfusion Sites: Busy, Level 1 trauma centers from within the LITES Network will be selected based upon the ability to enroll patients with the proposed inclusion and exclusion criteria who currently utilize initial ratio based resuscitation (1:1:1 or 1:1:2) for patients at risk of large volume transfusion and are able to perform all necessary requirements for the planned prospective cohort study proposed. There is the potential for sites to differ based upon their current massive transfusion protocol and these standard practices will be documented for each site.

Primary TBI Subgroup Stratification: Presence or absence of Traumatic Brain Injury (TBI) will be the principle subgroup stratification for the study. Presence of TBI will be based upon CT imaging results (classification: subarachnoid, subdural, intracerebral hemorrhage, intracranial injury, epidural, +/- shift, multifocal with specific classification) and TBI severity will be characterized and grouped by GCS, Abbreviated Injury Severity (AIS) coding, ICD-10 head region severity scores

Linking Investigations in Trauma and Emergency Services

Task Order 2: Shock, Whole blood and Assessment of TBI (SWAT)

and Rotterdam CT scores. The data coordinating center will collect de-identified serial head CT images (first two performed) from all participating sites in patients with a head abbreviated injury score of 2 or greater (head AIS >2). These images will allow the determination of Rotterdam CT head scores to appropriately classify traumatic brain injury severity. Serial head CTs (first two) will also be assessed for progression of injury. An independent and blinded neuroradiologist from the University of Pittsburgh will provide the classification of brain injury.

Due to the nature of the population being studied, there will be patients who have clinically evident TBI but who do not have a head CT completed due to clinical intervention being a higher priority than diagnostic imaging. Often when patients require urgent clinical interventions, diagnostic scans (including CTs) are deferred until the patient is stabilized and the emergent issue is resolved. Unfortunately, this means that sometimes a patient expires during intervention, and a CT is never obtained. Therefore, patients who present in extremis with a clinically obvious TBI (eg: unhelmeted motorcyclist, falls from height, etc.) will be included in the TBI sub-group even if they do not have head CTs completed.

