Sample Tracking, Management and Storage: After sample obtainment, processing and storage, samples will initially be batched sent to the University of Pittsburgh biological sample repository where it will be tracked, managed and stored until the necessary translational or mechanistic measurement are performed. The CCC and DCC have a long track record of coordinating such processes.

Power Analysis: The prospective cohort study will utilize time to 4 hour mortality for its primary outcome to power the study. Based upon the 6 LITES Network sites admission history that will be utilized and their respective volume of hemorrhagic shock patients meeting inclusion and exclusion criteria and a 3.5 year enrollment time period, we plan to initiate sampling on 1,050 patients over the enrollment time period of the study. With an 85% consent rate which is an estimate based upon prior studies of similar nature, we will consent for participation 892 patients for the study. With an estimate baseline rate of 4 hour mortality of 11.1 % derived from the PROPPR study, there will be 90% power to detect a hazard ratio of 1.9.

Calculations are based on the primary aim of the study based on the following assumptions:

- Type I error rate of 0.05
- Two-sided alternative hypothesis

Linking Investigations in Trauma and Emergency Services

Task Order 2: Shock, Whole blood and Assessment of TBI (SWAT)

- 6 sites will be involved, three whole blood and three component sites
- Each site will enroll 175 participants in 3.5 years of enrollment, of which, 85% will be eligible for the study (149)
- The calculations are based on Cox proportional hazard model
- A 4 hour event rate in the control (non-whole blood) group of 0.111

The power calculations for these secondary aims are presented below. When reporting the results of the analyses, caution will need to be taken with respect to the interpretation of the findings since they are secondary in nature.

The secondary outcomes in Aim 1B include binary outcome, continuous outcomes, and time to event outcomes. For the binary outcomes, the odds ratio that can be detected is presented in Table 1. For the continuous outcome, the effect size that can be detected is 0.13. Finally, for the time to event outcomes, the hazard ratio that can be detected over a range of event rates in the control group is also presented in Table 1.

Event Rate	.1	.2	.3	.4	.5	.6
Odds Ratio	1.76	1.56	1.49	1.46	1.46	1.48
Hazard Rate	2.69	1.70	.37	.30	.27	.30

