Hypothesis#1A: For the primary outcome, the time to death will be generated for each participant. Kaplan-Meier curves will be generated for each treatment group and a log-rank test will be used to compare the distribution of the cumulative proportion. A hierarchical Cox-proportional hazards regression model will be used to control for the within-institution clustering. The hierarchical Cox-proportional hazards regression model will then be used to assess the independent impact of whole blood on time to death after controlling for the clustering effect and potential confounding effects of baseline characteristics. The model will include main effects for whole blood usage and a propensity score for receiving whole blood. The propensity score for the use of whole blood will be generated using a boosted logistic regression model. The dependent variable in the model will be the use of whole blood and the independent variables will be the baseline characteristics of the population. The Cox-proportional hazards model will be used to estimate the cumulative probability of death 4 hours.

Hypothesis#1B: The analytic approach for the secondary outcomes included in Hypothesis#1B will vary based on the type of outcome. For binary outcomes (e.g., 12 hour and 24 hour mortality, death from exsanguination, incidence of MOF, nosocomial infection), the same analytic approach that was carried out for Hypothesis 1a will be implemented.

For continuous outcomes (e.g., transfusion ratios, blood transfusion requirements) a two-sided t-test for correlated means will be used to compare the means between those receiving and not receiving whole blood. A hierarchical analysis of variance model will be used to control for the within-institution clustering. The model will be used to assess the independent impact of whole blood after controlling for the clustering effect and the potential confounding. The model will include main effects for whole blood usage and propensity for receiving whole blood.

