model will be generated using the area under the curve as the dependent variable and the baseline characteristics as independent variables to generate an estimated area under the curve (propensity score) for each subject. The population will then be separated into five strata of equal sample size, based on the propensity. Within each stratum, the association of the area under the curve with outcome will be assessed using a hierarchical polytomous logistic regression model (outcome: GOS-E at six months, independent variable: area under the curve).

To determine the association across strata and if the association differs across strata, a multinomial polytomous regression model with GOS-E at six months as the outcome, area under the curve, an indicator of stratum, and the two-way interaction as independent variables will be fit.

The same analytic approach will be used to measure outcomes at discharge except a hierarchical logistic regression model will be used.

Subgroup Analysis: The general approach to assess the homogeneity of a treatment effect across subgroup will be to include an interaction term between the treatment variable and the characteristics defining the subgroup in the regression model. A statistically significant interaction term would indicate that the null hypothesis of a homogenous effect would be rejected indicating a differential effect of the treatment across the subgroups. For example, when examining the homogeneity of the effect of whole blood on the primary outcome among those with and without a traumatic brain injury, the hierarchical logistic model will be modified to include a main effect for traumatic brain injury and the two-way interaction between whole blood use and traumatic brain injury.

[figure not shown]

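### The whole-blood-by-TBI interaction model gives the propensity score one common slope, so confounding that differs by TBI can appear as, or mask, a difference in treatment effect

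*Combined protocol and SAP*

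**What the plan says.** The study is a "multicenter, prospective, observational cohort study over a 4 year period", so whole blood is not allocated at random. For the primary outcome, Analyses, Hypothesis#1A states: "The model will include main effects for whole blood usage and a propensity score for receiving whole blood". The score comes from one model: "The propensity score for the use of whole blood will be generated using a boosted logistic regression model". Its inputs are given only generically: "the independent variables will be the baseline characteristics of the population". TBI is not named among them.

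Primary TBI Subgroup Stratification states: "Presence or absence of Traumatic Brain Injury (TBI) will be the principle subgroup stratification for the study". To test whether the whole-blood effect differs by TBI, Subgroup Analysis has the model "modified to include a main effect for traumatic brain injury and the two-way interaction between whole blood use and traumatic brain injury". It reads a significant interaction as "indicating a differential effect of the treatment across the subgroups".

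No section provides a propensity-by-TBI term, covariate-by-TBI terms, a score fitted within TBI strata, or a balance check within those strata. The caveat in Predefined Subgroups that results are exploratory is attached to ten subsets listed as additional to the TBI analysis, so it does not clearly cover this test.

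**The concern.** A propensity score entered as one covariate removes confounding only if the score-to-outcome relation is modelled adequately. The TBI model lets the whole-blood effect vary by TBI but holds the score's slope equal. If the true slopes differ, one subgroup is under-adjusted and the other over-adjusted. The two errors go in opposite directions, and their difference falls on the interaction.

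Unequal slopes are plausible here. Classification of Mortality lists TBI/herniation separately from hemorrhage, so hemorrhage severity need not predict 4-hour death equally in both groups. Patients in extremis with clinically obvious TBI and no CT are placed in the TBI group, which ties membership to severity.

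At stake is the interpretation of the study's principal subgroup. An interaction produced by unequal confounding would be reported as a difference in treatment effect, and a real difference could be hidden.

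**Working it through.** **The plan's own figure.** No power or error rate is stated for the interaction. The nearest stated figure is 90% power for a hazard ratio of 1.9 with 892 patients (Power Analysis), where the plan sets "Type I error rate of 0.05", two-sided. Taking 11.1% as the whole-cohort rate gives 0.111 × 892 = 99 events. With 1:1 groups, z = ln(1.9) × √(99 × 0.25) − 1.96 = 0.642 × 4.975 − 1.96 = 1.23, so power is 0.89. The figure is reproduced, but it does not bear on the interaction.

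**Inputs from the documents.** 892 patients, 35% with TBI (0.35 × 892 = 312), 4-hour mortality 11.1%, three whole-blood and three component sites. Whole Blood Transfusion Sites implies a 33% whole-blood share instead.

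**Assumed inputs.** One standard-normal severity variable S. Its log-odds slope for receiving whole blood is a, and its log-odds slope for death is b. Both may differ by TBI. The documents give neither.

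**Why the common slope matters.** If the logit of the score is a·S and the logit of death is b·S, the slope of death on the score is b/a.

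- *Prognosis differs, selection is equal.* With b = 1.2 and 0.3, the required slopes are 1.2/a and 0.3/a, a fourfold difference. This holds whether or not the score contains TBI-by-severity terms.
- *Selection differs, prognosis is equal.* If the score lacks a TBI-by-severity term, it uses one pooled a in both groups, the required slopes are equal, and one slope is enough. If the score captures that term, the required slopes are b/a in each group and differ. With a = 0.5 and 0.3 they are 2b and 3.3b; with opposite signs of a they have opposite signs.

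**Simulation, no whole-blood effect in anyone** (logistic model, n = 892; chance of whole blood 0.5 × expit(1 + a·S), so it is available to half of the patients). The true interaction odds ratio is 1.

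| Scenario | Planned model | With propensity × TBI |
|---|---|---|
| Death slope 1.2 non-TBI, 0.3 TBI | 0.81–0.86; false positives about 8–9% | 1.00; 4–6% |
| Opposite selection, score captures TBI × severity | 0.71–0.76 | 0.97–1.02 |
| Opposite selection, score does not | 0.99–1.01 | not needed |
| Mild same-direction selection, such as 0.5 vs 0.3 | 1.02–1.08; about 5% | not needed |

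**Second simulation, common whole-blood odds ratio 1/1.9** (bias from 1,000,000 patients, error rates from 1,000 trials of 892, 50% whole blood; 33% is similar). The true interaction odds ratio is again 1, with Monte Carlo error of about 2%.

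- Equal confounding in both groups: 0.97, about 6%. No problem.
- Death slope 0.35 non-TBI, 1.05 TBI: 1.52, about 15%. With the added term: 0.97, about 6%. The direction reverses because TBI now has the steeper slope.
- Selection slope 0.35 vs 1.05: 0.64–0.67 and 10–12% if the score captures it; 0.96 and about 5% if it does not.
- Both slopes 0.35 vs 1.05: about 1.54 and 17% if the score omits TBI × severity; 0.96–1.03 if it captures it, because the two differences cancel.

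The size depends on the slopes and on how far severity, rather than site, decides who receives whole blood. With the added term, and a score that lets TBI modify its covariates, the second set returns to 0.96–0.98 with 3.7–6.3% false positives.

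**Re-estimating the score within TBI strata but keeping one slope.** Under opposite selection this gives ratios of 0.78 (a = 0.5/−0.4), 0.66–0.75 (0.8/−0.5) and 0.63 (1.2/−0.6), with 8–15% false positives. A stratum-specific score creates the unequal b/a that a single slope cannot fit.

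**The case against.** The strongest reply has four parts.

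*The text is illustrative.* Subgroup Analysis describes a general approach and gives TBI as an example. It does not name the propensity score or exclude further terms. This is correct: the common slope is inferred by reading the section as a modification of the Hypothesis#1A model. The alternative reading, with no score at all, would leave the interaction unadjusted.

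*Exposure is organised largely by site,* which limits how far severity can drive receipt. This also stands, and it is one reason for modest figures. It does not remove the prognostic route, because receipt can still depend on severity within whole-blood sites, where stock is limited.

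*A reader might infer a large, predictable false interaction,* for example because severity raises whole-blood receipt in non-TBI patients and lowers it in TBI patients. Nothing in the documents suggests such a reversal, and it distorts the result only if the score captures TBI-by-severity terms. Selection in the same direction with similar strength is negligible. A threefold contrast (0.35 vs 1.05) is not, but again only under that condition.

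*No numbered hypothesis rests on this test.* The principal TBI outcome is 6-month GOS-E, analysed under Hypothesis#1C with its own propensity-adjusted model. That lowers the priority. TBI nevertheless remains the principal subgroup, and the plan states how a significant interaction will be read.

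**Conclusion.** The concern holds as a possibility that the planned model leaves open. Confounding that differs by TBI can appear as, or mask, a difference in the whole-blood effect. The route that does not depend on how the score is built is a severity-to-death slope that differs by TBI: an interaction ratio of about 0.81–0.86 and false positives of about 8–9% under assumed slopes of 1.2 and 0.3. Differing selection matters only if the score captures TBI-by-covariate terms. The documents do not support saying that a false interaction will occur, or in which direction.

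These figures rest on assumed slopes, one confounder, a logistic model and no site clustering of outcome. Hypothesis#1A specifies a Cox model where Subgroup Analysis says logistic; that is a separate matter, and the argument about the slope applies to either. Priority: cheap improvement.

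**What to change.** For the TBI subgroup analysis, pre-specify a model with whole blood, TBI, whole blood × TBI, propensity score, and propensity score × TBI, and state that TBI is among the inputs of the score. Fitting the score separately within TBI strata is acceptable only together with a TBI-specific slope, not in place of it.

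The same term may be used for other subgroups defined before treatment, such as subsets 1–4 in Predefined Subgroups (origin of transfer and preinjury medication). It should not be prescribed for every subset. It does not repair subsets 5–7, which are defined by transfusion volume after treatment starts. In subset 8, leukocyte-reduced whole blood can be received only by whole-blood patients, so a treatment interaction is not estimable.

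The cost is one term, no new data, and a rise of about 0–5% in the standard error of the interaction (up to 7% in the more extreme contrasts). It should be written in before outcomes are examined, since adding it later would look data-driven.

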Interim Analysis: There will be two aspects of the interim analysis. First, for efficacy, the Lan and Demets approach will be utilized to conduct the interim efficacy analysis. This approach is preferable over other approaches because it is flexible to the number of interim analyses conducted during the course of the study. The Lan and DeMets approach requires the use of a spending function to allocate the type I error to the interim analysis. The O'Brien and Fleming spending function which minimizes the type I error allocated to the interim analysis, saving the vast majority for the primary analyses will be used. For the proposed interim analysis, assuming that 50% of the study will be completed, it is estimated that the type I error allocated to the interim analysis will be 0.005, leaving 0.048 of the type I error for the primary outcome analysis.

Linking Investigations in Trauma and Emergency Services

Task Order 2: Shock, Whole blood and Assessment of TBI (SWAT)

Time Line: The study will occur over a 4 year period with a 6 month start up period, an interim analysis at 2 years and a 3.5 year enrollment period.

Linking Investigations in Trauma and Emergency Services

Task Order 2: Shock, Whole blood and Assessment of TBI (SWAT)

BIBLIOGRAPHY

3. Hoyt DB. A clinical review of bleeding dilemmas in trauma. *Semin Hematol*. 2004;41(1 Suppl 1):40-43.

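### The stated interim and final levels of 0.005 and 0.048 are not those of the named Lan-DeMets spending function, and the 2-year look is not tied to 50% of the information

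*Combined protocol and SAP*

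**What the plan says.** The Power Analysis section of the combined protocol and SAP sets "Type I error rate of 0.05" with a "Two-sided alternative hypothesis". Under Interim Analysis, "the Lan and Demets approach will be utilized to conduct the interim efficacy analysis". The function is named: "The O'Brien and Fleming spending function which minimizes the type I error allocated to the interim analysis". The section then gives an interim figure: "assuming that 50% of the study will be completed, it is estimated that the type I error allocated to the interim analysis will be 0.005". The level for the final test comes in the same sentence: "leaving 0.048 of the type I error for the primary outcome analysis".

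The Time Line, directly after, describes a 4-year study with "a 6 month start up period, an interim analysis at 2 years and a 3.5 year enrollment period".

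The primary analysis (Analyses, Hypothesis #1A) is a log-rank test followed by a hierarchical Cox model for death by 4 hours. The plan gives neither an event count for the look nor a definition of the information fraction. It does not say which form of the spending function is meant, or that the levels will be recomputed at the fraction actually observed.

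**The concern.** A spending function fixes how much type I error may be used at a given information fraction. Once function, total error and fraction are named, the interim and final levels follow. Here all three are named and the stated levels are not the ones that follow.

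The fraction is itself uncertain. Half of the study can mean half of calendar time, enrollment or deaths. These differ under the plan's own Time Line, and only deaths measure information for a log-rank or Cox analysis.

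At stake is the threshold for an early efficacy claim. A statistician who takes the printed figure would use 0.005. One who computes the named function would use about 0.003 or 0.006 at 50%, and something else at another fraction. The plan does not say which governs.

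**Working it through.** **Inputs.** Total two-sided error 0.05 (Power Analysis); two looks, O'Brien-Fleming-type Lan-DeMets spending, assumed fraction t = 0.50, stated levels 0.005 and 0.048 (Interim Analysis); start-up 0.5 year, look at 2 years, enrollment 3.5 years, study 4 years (Time Line); 1,050 patients sampled (Power Analysis). The two test statistics are taken as bivariate normal with correlation √t, and final levels are solved so that the overall two-sided error is 0.05.

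**1. Reproducing the stated pair.** The classical O'Brien-Fleming boundary for two equally spaced looks has critical values c/√0.5 and c, with c chosen to give 0.05 overall. This gives c = 1.977 and an interim value of 2.797, hence two-sided levels of 0.0052 and 0.0480. To three decimals that is 0.005 and 0.048.

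**2. The named function at 50%.** Two forms are in common use.

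- Per-side form: α(t) = 4[1 − Φ(2.2414/√t)]. At t = 0.50 it spends 0.0031, and the final level is 0.0490.
- Two-sided form: α(t) = 2[1 − Φ(1.96/√t)]. At t = 0.50 it spends 0.0056, and the final level is 0.0478.

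Neither gives 0.005 with 0.048. The per-side form spends 0.005 at about t = 0.55, the two-sided form at about t = 0.49.

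**3. Where the 2-year look falls.** This step assumes uniform accrual.

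- Calendar time: 2/4 = 50%.
- Enrollment, clock from study start: (2 − 0.5)/3.5 = 1.5/3.5 = 42.9%, or 450 of 1,050. This is the natural reading, because 0.5 + 3.5 = 4 years.
- Enrollment, clock from first enrollment: 2/3.5 = 57.1%, or 600 of 1,050.

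Neither clock gives 525 of 1,050. With a 4-hour endpoint there is almost no lag, so deaths should track enrollment if the death rate is stable, but the plan gives no death count to confirm this.

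**4. Levels at each fraction, and overall error if 0.005 and 0.048 were used as nominal levels.**

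| Fraction | Per-side form, interim / final | Two-sided form, interim / final | Overall error of 0.005 / 0.048 |
|---|---|---|---|
| 43% | 0.0012 / 0.0496 | 0.0028 / 0.0489 | 0.0504 |
| 50% | 0.0031 / 0.0490 | 0.0056 / 0.0478 | 0.0499 |
| 57% | 0.0061 / 0.0481 | 0.0095 / 0.0463 | 0.0495 |

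An interim level of 0.005 corresponds to |Z| = 2.81. At 43% the two forms require 3.23 and 2.99, so 0.005 would be looser. At 57% they require 2.74 and 2.59, so 0.005 would be stricter.

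**The case against.** The strongest defense is that the stated pair works at the fraction assumed for it. At 50% its overall error is 0.0499, and if 0.005 is spent there the matching final level is 0.0481, so 0.048 is right as a nominal level. The text calls the figure an estimate, and Lan-DeMets boundaries are by nature computed at the observed fraction. The two-sided form at 50% is slightly looser than 0.005, so the printed figure is not lax against every version of the function. The plan also speaks of half of the study, and 2 of 4 years is half, so its two statements agree on a calendar reading. All of this stands, and it limits the point.

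Three stronger readings are tempting and not supported.

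- A reader might infer inflated type I error, perhaps by adding 0.005 and 0.048 to get 0.053. The looks are correlated and 0.048 is a nominal final level, not the remainder of 0.05. The overall error is 0.0499 at 50% and 0.0504 at 43%.
- A reader might infer that the interim test is about 2 to 4 times too loose (0.005/0.0028 = 1.8; 0.005/0.0012 = 4). That needs both a 43% look and a frozen 0.005. The plan fixes neither, and at 57% the direction reverses.
- A reader might infer that the look is simply at 43%. That depends on the clock and on uniform accrual, and the Study Setting and Whole Blood Transfusion Sites sections allow sites to be added over time.

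The defense does not remove the mismatch. Even as an estimate at its own assumed 50%, 0.005 with 0.048 is not what either form of the named function gives. The flexibility the section cites concerns the number of looks, and recomputation at the observed fraction is nowhere stated. Calendar time explains the 50% but is not the information scale of the primary analysis.

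**Conclusion.** The point holds as a specification error of modest size. The plan names one procedure and prints the levels of another: 0.005 and 0.048 belong to the classical O'Brien-Fleming boundary, while the named function gives 0.0031 and 0.0490 or 0.0056 and 0.0478 at 50%, depending on a form the plan does not state. The 2-year look is 50% of calendar time only. With uniform accrual it is about 43% of enrollment on the natural clock or 57% on the other, and the fraction of deaths is undefined.

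Control of the overall type I error is not in question. What is unsettled is the interim efficacy threshold: if 0.005 were applied at a 43% look it would exceed what the function allows (0.0012 or 0.0028), and at 57% it would fall short of it (0.0061 or 0.0095). The levels rest on two looks and a two-sided 0.05; the enrollment fractions rest on uniform accrual and on the clock chosen.

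**What to change.** In the Interim Analysis and Time Line sections:

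1. Define the information fraction as observed over planned 4-hour deaths, and state the planned number.
2. Reconcile the 2-year look with the 50% assumption, either by triggering the look at 50% of planned deaths or by keeping 2 years and stating the fraction expected then.
3. Name the form of the spending function and replace 0.005 and 0.048 with its levels (per-side form at 50%: 0.0031 and 0.0490). Alternatively, state that the classical O'Brien-Fleming boundary is used.
4. Describe the second figure as the nominal final level.
5. State that the boundary will be recomputed at the observed fraction.

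The cost is a wording change and a slightly different, probably stricter, interim threshold. A look triggered by deaths also gives up a fixed calendar date.
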